6.3 Other Eligibility Criteria Considerations

- All patients and/or their parents or legal guardians must sign a written informed consent (and assent when applicable)
- Patients and/or parents who are unable to read at a grade 2 level will be excluded from the patient-reported outcome components of the study, as will non-English speaking patients and/or parents when there is no availability of translated versions in their spoken language(section 9.3). They will not be excluded from all other aspects of the study

7 CONCURRENT MEDICATIONS

All subjects should be maintained on the same medications throughout the entire study period, as medically feasible, with no introduction of new chronic therapies.

7.1 Allowed Medications and Treatments

7.1.1 If necessary, rescue medications are allowed as detailed in the protocol.
See section 8.3.

7.1.2 Supportive care medications

Use of hormonal therapies and anti-fibrinolytic agents is allowed, but must be documented on appropriate case report forms (CRFs).

7.2 Prohibited Medications and Treatments

7.2.1 The use of second-line platelet-enhancing therapies in weeks 1-12 is not allowed and will result in coming off protocol therapy (*i.e. subjects will discontinue eltrombopag if on study med, but subjects will continue to be followed on study for data collection*). In the event of severe or uncontrolled bleeding (Buchanan Bleeding Score of 4 or 5) requiring an emergency intervention listed below during weeks 1-12, the patient will come off protocol therapy. The following medications/procedures are prohibited during the first 12 weeks of the study:

- Dexamethasone

- Rituximab
- Mercaptopurine
- Azathioprine
- Dapsone
- Sirolimus
- Cyclosporine
- Mycophenolate
- Romiplostim
- Vinca alkaloids
- Cyclophosphamide
- Splenic artery embolization
- Splenectomy
- Other medications besides prednisone, IVIg, and anti-D thought to be active in the treatment of ITP

The use of these medications/procedures after week 12 for patients not currently taking eltrombopag (patients in the standard treatment arm, or patients in the eltrombopag arm who are non-responders and have been taken off investigational drug) is at the discretion of the treating physician, but must be reported on appropriate CRFs.

7.2.2 Other non-platelet-enhancing therapies (other than those described in section 7.1.2) are not allowed in weeks 1-12 and would be a protocol violation if used:

- Desmopressin acetate (DDAVP)
- Recombinant Factor VIIa
- Platelet transfusion

7.2.3 Patients taking anti-platelet agents (including aspirin, NSAIDs, or clopidogrel) or anticoagulants (including heparin, warfarin, or direct oral anticoagulants) are prohibited from enrolling, and these medications are not allowed during the study.

7.3 Concomitant medications and interactions with eltrombopag

The patient must be told to notify the investigational site about any new medications he/she takes after the start of the study treatment. Site study personnel should verify that there are no interactions with protocol therapy, as described in this section of the protocol. If an adjustment in eltrombopag dose is required due to a concomitant medication, that should be noted on the eltrombopag dosing CRF.

Any medications administered during the study given for the purpose of treating or preventing bleeding (such as hormonal therapies or antifibrinolytic agents), or that

are prohibited due to antiplatelet or antithrombotic effects (such as NSAIDs, aspirin, or anticoagulants), or that are thought to have effect in ITP must be listed on the Concomitant Medications eCRF.

HMG-CoA Reductase Inhibitors (statins)

Patients will be permitted to use HMG-CoA reductase (3-hydroxy-3-methyl-glutaryl-CoA) inhibitors during the study, but these drugs should be used with caution and a 50% dose reduction of the HMG-CoA reductase inhibitor is recommended, with close monitoring for safety, such as liver chemistry and signs and symptoms of myolysis, and efficacy, such as cholesterol and triglycerides (refer to individual product information for monitoring recommendations).

Polyvalent Cations (Chelation)

Eltrombopag chelates with polyvalent cations such as aluminum, calcium, iron, magnesium, selenium and zinc. Eltrombopag should be taken at least two hours before or four hours after any products such as antacids, dairy products, or mineral supplements containing polyvalent cations to avoid significant reduction in eltrombopag absorption.

Food Interaction

The administration of a single 50 mg-dose of eltrombopag with a standard high-calorie, high-fat breakfast that included dairy products led to reduced eltrombopag exposure. Foods low in calcium (defined as <50 mg calcium per serving) including fruit, lean ham, beef and unfortified (no added calcium, magnesium, iron) fruit juice, unfortified soy milk, and unfortified grain did not significantly impact plasma eltrombopag exposure, regardless of calorie and fat content. To avoid significant reduction in eltrombopag absorption, eltrombopag should be taken at least two hours before or four hours after food containing > 50 mg calcium and at least one hour before to two hours after food containing little (< 50 mg) (or preferably no) calcium.

Patients must abstain from using investigational or not marketed drugs without a well-known safety profile and from using prohibited prescription or nonprescription drugs within 7 days or 5-half-lives (whichever is longer) prior to the first dose of study treatment and until completion of follow-up procedures unless, in the opinion of the Investigator and Sponsor, the medication will not interfere with the study (see Section 6.2 Exclusion Criteria).

Patients must abstain from taking herbal supplements within 7 days (or 14 days if the drug is a potential enzyme inducer) or 5-half-lives (whichever is longer) prior to the first dose of study treatment until completion of the 30-day follow-up period, unless the Investigator and Sponsor agree that the medication will not interfere with the study treatment.

Any other TPO-R agonists are prohibited for patients on eltrombopag (e.g. romiplostim).

Substrates of OATP1B1 or BCRP

Concomitant administration of eltrombopag and other OATP1B1 or BCRP substrates should be undertaken with caution.

Examples of OATP and BCRP substrates

OATP Substrates

aliskiren, ambrisentan, anacetrapib, atenolol, atrasentan, atorvastatin, bosentan, bromocriptine, caspofungin, cerivastatin, celiprolol, danoprevir, empagliflozin, ezetimibe, fimasartan, fexofenadine, fluvastatin, glyburide, maraviroc, SN-38, rosuvastatin, simvastatin acid, pitavastatin, pravastatin, repaglinide, rifampin, valsartan, olmesartan, telmisartan, montelukast, ticlopidine.

BCRP Substrates

atorvastatin daunorubicin, doxorubicin, hematoporphyrin, imatinib, methotrexate, mitoxantrone, pitavastatin, rosuvastatin, SN-38 (irinotecan), ethinyl estradiol, simvastatin, sulfasalazine, sofosbuvir, topotecan, sulfasalazine

OATP1B1 and OATP1B3 substrates and inhibitors are combined into one list due to the following reasons, (1) over-lapping substrate and inhibitor specificity and (2) lack of clinical evidence implicating the sole involvement of either OATP in the observed PK interaction.

8 TREATMENT PLAN

8.1 Overview of Treatment Plan

According to the randomized treatment group assignment, patients will be treated with either eltrombopag as a single agent or physician's choice of standard therapy.

8.2 Investigational Product Dosage/Administration

8.2.1 Standard first-line therapy

Subjects randomized to the standard therapy arm will receive one of three treatments at the discretion of the treating physician. Patients who previously failed standard management prior to study entry must be treated with a different agent than their original failed agent. *e.g. Patient who failed steroids could receive either IVIg or anti-D if randomized to the standard treatment arm.*

Standard therapy will be administered as commercially available drug.

Investigator may choose amongst the following:

8.2.1.1 **IVIg:** IVIG 1 g/kg x1¹⁸ (no steroids for pre-medication or adjunctive therapy)

8.2.1.2 **Steroids:** Prednisone/Prednisolone 4 mg/kg/day (Max 120 mg/day) x 4 days¹⁹

8.2.1.3 **Anti-D:** Anti-D globulin 75 mcg/kg x1¹⁸ (no steroids for pre-medication or adjunctive therapy)

Table 8A Standard therapies

Treatment	Dose	Route	Duration
Prednisone/Prednisolone	IVIg 1 g/kg (round to closest vial size without exceeding 1g/kg)	IV	1 dose
	Prednisone/Prednisolone 2 mg/kg/dose BID (max 120 mg/day)	PO	4 days
	Anti-D globulin 75 mcg/kg (round to closest vial size without exceeding 75 mcg/kg)	IV	1 dose

8.2.2 **Eltrombopag**

Patients randomized to eltrombopag will be treated for 12 weeks, with the possibility to continue therapy for up to 1 year depending on response. Instructions for titrating dose during the first 12 weeks and during weeks 13-52 are given below.

8.2.2.1 **Dose initiation**

Starting dose for eltrombopag will be based on manufacturer recommendations, and drug will be titrated to effect per guidelines, modified as below

- Children 1 to 5 years: Initial: 25 mg once daily
- Children ≥6 years and Adolescents: Initial: 50 mg once daily (25 mg once daily for patients of East-Asian ethnicity [e.g., Chinese, Japanese, Korean, Taiwanese])
- Dose should be titrated based on platelet response. Maximum dose: 75 mg once daily. Dose should be adjusted only after 2 weeks on the prior dose (unless holding for thrombocytosis)
- Adjust dose based on platelet response (Table 8B, below)

8.2.2.2 **Dosage adjustment based on platelet response weeks 1-12**

Table 8B Dose adjustment during weeks 1-12 of study

PLATELET COUNT RESULT	DOSE ADJUSTMENT OR RESPONSE
------------------------------	------------------------------------

< 50 x 10⁹/L following at least 2 weeks of eltrombopag	
Increase daily dose by 25 mg to a maximum of 75 mg/day.
 
For patients taking 12.5 mg once daily, increase the dose to 25 mg daily before increasing the dose amount by 25 mg.

≥ 50 x 10⁹/L to < 200 x 10⁹/L	Continue current dose
≥ 200 x 10⁹/L to ≤ 400 x 10⁹/L at any time	
Decrease the daily dose by 25 mg. Wait 2 weeks to assess the effects of this and any subsequent dose adjustments.
 
For patients taking 25 mg once daily, decrease the dose to 12.5 mg once daily.
 
For patients taking 12.5 mg once daily, discontinue eltrombopag.

> 400 x 10⁹/L at any time	
Hold eltrombopag; increase the frequency of platelet monitoring to twice weekly.
 
Once the platelet count is < 200 x 10⁹/L, reinitiate therapy at a daily dose reduced by 25 mg. For patients taking 25 mg once daily, reinitiate therapy at a daily dose of 12.5 mg.
 
If platelets remain ≥ 200 x 10⁹/L to <400 x 10⁹/L after 2 weeks, decrease frequency of platelet checks to weekly.

> 400 x 10⁹/L after 2 weeks of therapy at lowest dose of eltrombopag	
Discontinue eltrombopag.
 
If platelets drop to <50 x 10⁹/L after discontinuing eltrombopag, restart at the last effective dose (lowest dose that achieved platelet count ≥ 50 x 10⁹/L)

Please note: while platelets are checked weekly per study requirements, adjustments are made at time intervals described in the table

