8.2.2.6 Dosing Guidelines

Administer on an empty stomach, 1 hour before or 2 hours after a meal. Do not administer concurrently with antacids, foods high in calcium, or minerals (e.g., iron, calcium, aluminum, magnesium, selenium, zinc); separate by at least 4 hours.

TABLETS MUST BE SWALLOWED WHOLE.

Eltrombopag for oral suspension delivered 22% higher plasma AUC0-INF than the tablet formulation. When switching between the oral suspension and tablet, closely monitor platelet counts.

If vomiting occurs within 30 minutes of dose, dose should be re-administered.

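### In weeks 1-12, section 8.2.2.1 and Table 8B require opposite actions at platelets of 200-400 x 10⁹/L before day 14 on a dose; sections 7.3 and 8.2.2.6 also differ, more narrowly, on spacing from calcium and minerals

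*Combined protocol and SAP*

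**What the plan says.** **Timing of dose changes.** Section 8.2.2.1 (Dose initiation) gives a general rule: "Dose should be adjusted only after 2 weeks on the prior dose (unless holding for thrombocytosis"). Its next bullet sends the reader to Table 8B for adjustment by platelet response.

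Table 8B, in section 8.2.2.2, covers weeks 1-12. The row "≥ 200 x 10⁹/L to ≤ 400 x 10⁹/L at any time" carries the instruction "Decrease the daily dose by 25 mg. Wait 2 weeks to assess the effects of this and any subsequent dose adjustments". In the same row, a patient on 25 mg goes to 12.5 mg and a patient on 12.5 mg stops. The row for counts above 400 x 10⁹/L has a different action: "Hold eltrombopag; increase the frequency of platelet monitoring to twice weekly". The row for low counts applies "following at least 2 weeks of eltrombopag". A note under the table reads: "Please note: while platelets are checked weekly per study requirements, adjustments are made at time intervals described in the table".

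**Spacing from calcium and minerals.** Section 7.3 says "Eltrombopag should be taken at least two hours before or four hours after any products such as antacids", and extends this to dairy products and mineral supplements. It repeats the same two limits for food with more than 50 mg of calcium. Section 8.2.2.6 covers antacids, high-calcium foods and minerals and says "separate by at least 4 hours", with no distinction between before and after.

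**The concern.** Section 8.2.2.1 is restrictive: it uses the word *only* and names a single exception. The 200-400 row of Table 8B is equally firm in the other direction. An investigator with such a count early on a dose cannot obey both. Two sites could each cite the protocol and treat the same child differently.

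This touches a part of the regimen that the sponsor designed on purpose. Section 2.2 says that dose adjustment after a platelet response departs from the label because of rebound thrombocytopenia when drug is held. The affected arm is the experimental one (108 planned patients, section 16.f). Section 13 asks for deviations to be reported within 5 days and ties them to significant requirements, including those on subject safety and the primary endpoint. Where two rules conflict, the same dosing decision can be classed as compliant or as a deviation.

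The spacing rules matter less, but section 7.3 itself presents them as a protection against a significant loss of absorption.

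**Working it through.** The plan gives no figure to reproduce here. The check applies each pair of rules to the same patient.

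**1. Dose timing, weeks 1-12**

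| Situation | Section 8.2.2.1 | Table 8B | Agree? |
|---|---|---|---|
| Count 200-400, fewer than 14 days on dose | No adjustment yet | Reduce now (stop if on 12.5 mg) | **No** |
| Count 200-400, 14 days or more on dose | Adjustment allowed | Reduce | Yes |
| Count above 400, any day | Hold is exempt from the wait | Hold | Yes |
| Count below 50 (increase) | After 2 weeks | After at least 2 weeks | Broadly yes |

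Only the first line conflicts.

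**2. Does the exception for holding cover that line?** No. Table 8B treats holding as a separate action, with its own restart rule, for counts above 400. The 200-400 row calls for a reduction, or for stopping at the lowest dose.

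**3. When can the conflict arise?** After a reduction, Table 8B imposes its own 2-week wait, which matches section 8.2.2.1. That leaves mainly the first 14 days after starting and after an increase; a restart after a hold can raise the same question. The stop instruction at 12.5 mg is a rarer case. Starting doses are 25 mg or 50 mg, so a patient is on 12.5 mg only after a reduction or a restart.

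**4. How far apart can the two rules act?** The gap is 14 days minus the days on the dose when the count is taken. The procedures table in section 9 is partly broken in the text available, so it is assumed that platelets are counted at the 72-hour and week 1 visits.

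- Count at 72 hours: 14 − 3 = 11 days. The ±24-hour window puts the count on days 2 to 4, giving 12 to 10 days.
- Count at week 1: 14 − 7 = 7 days. The ±72-hour window puts the count on days 4 to 10, giving 10 to 4 days.
- Count one week after an increase, under the weekly checks in the note to Table 8B: 7 days.
- Later in the period, the listed visits from week 4 are two weeks apart. If an increase is made at one visit and the next count comes at the following visit, the gap is 14 − 14 = 0 days.

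**5. Spacing**

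| Eltrombopag taken | Section 7.3 | Section 8.2.2.6 | Agree? |
|---|---|---|---|
| Less than 2 h before the product | Not allowed | Not allowed | Yes |
| At least 2 h but under 4 h before | Allowed | Not allowed | **No** |
| 4 h or more before | Allowed | Allowed | Yes |
| Less than 4 h after | Not allowed | Not allowed | Yes |
| 4 h or more after | Allowed | Allowed | Yes |

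The difference is one window of 4 − 2 = 2 hours, on one side of the dose. A family keeping 4 hours on both sides meets both sections.

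**The case against.** The best defence is that the protocol already shows which text to use for timing. Section 8.2.2.1 is headed as dose initiation, and section 8.2.2.2 as adjustment by platelet response. The bullet after the 2-week rule points to Table 8B, and the note under the table refers the reader to the table's intervals. A sensible site might conclude that the table governs. That argument has weight, but it leaves the conflict standing: neither the bullet nor the note withdraws the word *only* or widens the exception. The note can also be read as explaining merely why weekly counts do not lead to weekly changes.

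Three further objections stand and limit the point:

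- A reader might infer that following either text always breaches the other. For spacing this is not so. Section 8.2.2.6 is the stricter minimum, and meeting it also meets section 7.3.
- A reader might infer that spacing differences will produce deviations that cannot be judged consistently. The documents do not support this. Section 8.7 measures compliance by missed doses and pill counts, and no section describes recording the timing of meals or minerals.
- A reader might infer an effect on the primary result. The conflict arises at counts of 200-400, well above the response threshold of 50 x 10⁹/L. After a start at day 0 it falls before the week 6-12 assessment period. The documents show neither how often it would occur nor any bias between arms.

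**Conclusion.** The dose-timing contradiction is real and is in the operative text. For counts of 200-400 x 10⁹/L in weeks 1-12 with fewer than 14 days on the current dose, no action satisfies both section 8.2.2.1 and Table 8B. It does not extend to increases, to counts above 400, or to patients already 14 days on a dose.

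Under the assumed visit counts, the two rules act about 7 to 11 days apart at nominal visit times. A full 2 weeks is an outer bound, since a count must be taken before either rule applies; unscheduled counts could change the gap.

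The spacing mismatch is minor: a 2-hour window before the product, avoidable by keeping the longer gap.

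The documents give no frequency for either case, so no effect on response rates, power or the treatment comparison can be derived, and none is asserted. The case for correction is that a dosing instruction cannot be followed as written.

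**What to change.** The sponsor should reconcile section 8.2.2.1 with Table 8B, and section 7.3 with section 8.2.2.6, so that each instruction is stated once and other sections only refer to it. For dose timing, the revised text should say explicitly how the 2-week rule relates to the 200-400 row, including the stop instruction at 12.5 mg, and what the exception for holding covers. Sites should be told of the clarification so that dosing and deviation reports follow one text. Which timing or spacing rule is right is for the clinical team.

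The cost is protocol wording, with the IRB approval that section 18.a requires for an amendment, and a memo to sites. Sample size, endpoints and analysis do not change.

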8.2.2.3 Eltrombopag Stopping Criteria for Non-Responders

Discontinue eltrombopag if platelet count <30 x10⁹/L after 4 weeks at the maximum daily dose of 75 mg. *Non-responders will come off protocol therapy, but will continue on study for data collection through duration of 1 year from date of consent.*

8.2.2.4 Weaning weeks 13-52

For patients who have completed 12 weeks of eltrombopag and maintain a platelet count $\geq 100 \times 10^9/L$, eltrombopag will be weaned, by dose reducing 12.5mg q2 weeks per guidelines in table 8C below (with treating physicians exercising clinical judgement with respect to wean in the context of the patient's status, including intercurrent infections).

Patients who have been unable to be weaned off of eltrombopag by 1 year will discontinue study drug. Continuation on commercially available eltrombopag at that point is at the discretion of the investigator.

Table 8C Modified dose adjustment during weeks 13-52 of study

PLATELET COUNT RESULT	DOSE ADJUSTMENT OR RESPONSE
$< 30 \times 10^9/L$ 2 weeks after dose adjustment	Increase dose to last effective dose (to attain platelet count $\geq 30 \times 10^9/L$)
$\geq 30 \times 10^9/L$ to $< 100 \times 10^9/L$	Continue current dose.
$\geq 100 \times 10^9/L$ to $< 200 \times 10^9/L$	Decrease daily dose by 12.5 mg. Wait 2 weeks to assess the effects of this and any subsequent dose adjustments. If platelets remain $\geq 100 \times 10^9/L$ after 2 weeks at lowest dose, discontinue eltrombopag.
$\geq 200 \times 10^9/L$ to $\leq 400 \times 10^9/L$	Decrease the daily dose by 25 mg. Wait 2 weeks to assess the effects of this and any subsequent dose adjustments. For patients taking 25 mg once daily, decrease the dose to 12.5 mg once daily. For patients taking 12.5 mg once daily, discontinue eltrombopag.
$> 400 \times 10^9/L$	Discontinue eltrombopag
$< 30 \times 10^9/L$ after weaning off eltrombopag	Restart at the last effective dose (lowest dose prior to weaning). If platelets remain $< 30 \times 10^9/L$, increase per initial dose adjustment.

8.2.2.5 Dose Modification for toxicities

LFTs (AST, ALT, Tbili) will be monitored every 2 weeks during the first 12 weeks of study, then monthly for patients continuing on eltrombopag.

Repeat abnormal liver function tests within 3 to 5 days; if confirmed abnormal, monitor weekly until resolves, stabilizes, or returns to baseline.

If ALT levels ≥ 3 times the upper limit of normal (ULN) in patients with normal hepatic function at baseline or ≥ 3 times baseline (or > 5 times ULN; whichever is lower) in those with preexisting transaminase elevations: Discontinue treatment.

If Tbili >1.5 times the upper limit of normal (ULN) contact the study PI to discuss management.

Eltrombopag must be permanently discontinued if any of the following events occur or is identified at any time during the study:

- Cytogenetic abnormalities
 - Monosomy 7 – discontinue eltrombopag
 - Other abnormalities – discontinuation at physician discretion
- Thromboembolism considered related to drug occurs
- Development of MDS or AML
- Difficulties to continue the study treatment due to AE(s)

Subjects who experience a deep venous thrombosis (other than a line-related upper extremity thrombosis) or a pulmonary embolus, a transient ischemic attack or stroke, or a myocardial infarction at any time while on eltrombopag will discontinue eltrombopag.

8.2.2.6 Dosing Guidelines

Administer on an empty stomach, 1 hour before or 2 hours after a meal. Do not administer concurrently with antacids, foods high in calcium, or minerals (e.g., iron, calcium, aluminum, magnesium, selenium, zinc); separate by at least 4 hours.

TABLETS MUST BE SWALLOWED WHOLE.

Eltrombopag for oral suspension delivered 22% higher plasma AUC0-INF than the tablet formulation. When switching between the oral suspension and tablet, closely monitor platelet counts.

If vomiting occurs within 30 minutes of dose, dose should be re-administered.

